### Supportive Care Measures

- Prophylactic use of G-CSF is strongly recommended for subjects assigned to the combination arm (Arm A).
- Subjects may be enrolled into the study while receiving recombinant erythropoietin provided they have received recombinant erythropoietin for at least 4 weeks before the first dose of study drug.
- Subjects may continue receiving hormone replacement therapy while on study.
- Subjects may receive pyridoxine (vitamin B6) at 200 mg by mouth daily to help prevent HFS due to DOXIL. If given, treatment should begin before Day 1, Cycle 1.
- All subjects receiving DOXIL should be cautioned to avoid vigorous activity, pressure on the skin, and exposure to extreme heat, hot water, and sun to reduce HFS-related symptoms.

For any concomitant therapy administered as a treatment for a new condition or a worsening of an existing condition, the condition must be documented on the adverse events page in the CRF.

## 9. STUDY EVALUATIONS

Following Amendment 6, study data collection will cease when all subjects on study treatment have completed the treatment termination visit assessments as specified in the Time and Events Schedule for Amendment 6 or by 18 January 2018, whichever occurs first. For subjects continuing treatment with single-agent DOXIL, as per the local standard of care, only serious adverse events should be reported to JR&D as outlined in Section 12.3.2.

### 9.1. Study Procedures

#### 9.1.1. Overview

The Time and Events Schedule for Amendment 6 summarizes the treatment termination visit assessments.

All visit-specific PRO assessments during a visit should be conducted before any tests, procedures, or other consultations for that visit to prevent influencing subject perceptions.

Additional serum or urine pregnancy tests may be performed, as determined necessary by the investigator or required by local regulation, to establish the absence of pregnancy at any time during the subject's participation in the study.

The blood volumes collected from each subject for laboratory evaluations throughout this study are approximately 15 mL for screening serum chemistry and hematology tests; 10 mL for BRCA 1/2 testing at screening (for subjects who do not have a known BRCA 1/2 status); 4 mL for subjects consenting to the optional pharmacogenomics component of the study (where local regulations permit); 45 mL and 60 mL for treatment Arms A and B, respectively, per cycle for serum biochemistry and hematology tests; 4 mL per scheduled CA-125 sample; and 24 mL from those subjects who provide PK samples. Repeat or unscheduled samples may be taken for safety reasons.

### 9.1.2. Screening Phase

Informed consent must be obtained before the conduct of any protocol-specific procedure. All screening procedures must be completed and results obtained, where applicable, before random assignment to treatment. It should be noted, however, that clinical assessments performed as part of the subject's routine clinical evaluation and not specifically for this study need not be repeated after signed informed consent has been obtained, provided that these assessments fulfill the study's requirements.

The Screening Phase begins with the signing of the informed consent and should not last longer than 30 days. During the Screening Phase, the medical monitors will confirm subject eligibility based on previous therapy history, according to inclusion criteria #4 through #8 [Section 4.1, Inclusion Criteria]). Response to second-line platinum-based therapy will be confirmed either based on imaging demonstrating at least a 30% decline in tumor burden or a 50% reduction of elevated baseline serum CA-125 levels ( $\geq 2 \times$  ULN, measured within approximately 4 weeks prior to the first dose of second-line platinum-based therapy that is maintained after at least 28 days as modified from Gynecologic Cancer Intergroup [GCIG] criteria [[Attachment 1](#)]).

A complete medical history and review of systems will be taken, including concomitant medications, prior therapy, and a description of key features of the disease including disease histology. Each subject must have an ECG and LVEF assessment (MUGA scan or 2D-ECHO) to document the LVEF is within normal range according to the institutional guidelines. A physical examination (including vital signs, weight, and height) will be performed, and BSA will be calculated either during screening or on Day 1 of Cycle 1. Laboratory evaluations (CA-125 measurement at a local laboratory, hematology and serum chemistry) will be done, and a urine or serum pregnancy test will be done for women of childbearing potential. Eastern Cooperative Oncology Group performance status will be assessed. BRCA 1/2 status will be collected on the CRF for subjects who have previously been tested for BRCA 1/2 mutations. For subjects who do not have a known BRCA 1/2 status, a blood sample will be collected to determine BRCA 1/2 status during the screening phase. It is expected that BRCA 1/2 analysis will require approximately 10 to 14 days. In the case of delayed BRCA 1/2 mutation reporting, the screening period may be extended for up to 14 days (with medical monitor approval). In such cases, only

screening clinical laboratory assessments (hematology, clinical chemistry, and liver panel) will need to be repeated. On Day 1 of Cycle 1, subjects will also be offered the option of providing a whole blood sample for pharmacogenomics analysis. Subject participation in the pharmacogenomic research component of the study is voluntary and refusal to participate will not result in ineligibility for the main part of the study. Consent for this is independent of the subject's consent for the main body of the study. Either consent or refusal to participate in the pharmacogenomic analysis must be documented within the pharmacogenomics consent form.

Screening procedures to be completed within 30 days before randomization include:

- Signed informed consent (including the optional pharmacogenomics informed consent, where applicable).
- Review of eligibility criteria
- Review of medical history and demographics
- Review of prestudy therapy
- Review of preplanned surgery/procedures(s)
- LVEF assessment (MUGA or 2D-ECHO) and ECG
- Tumor assessments, including radiographic imaging of the chest (with lung views), abdomen, and pelvis.
- BRCA 1/2 status (In case of delayed BRCA 1/2 mutation reporting, the screening period may be extended for up to 14 days, with medical monitor approval.)
- Pregnancy testing
- Physical examination
- Vital signs
- ECOG performance status
- Laboratory tests including CA-125, hematology, and clinical chemistry
- Review of concomitant therapy
- Review of adverse events
- Submission of redacted source documents supporting subject eligibility relevant to inclusion criteria #4 through #8.
- On or prior to Day 1 of Cycle 1, all subjects will be provided with a “wallet (study) card” and instructed to carry this card with them for the duration of the study.

### **9.1.3. Open-Label Treatment Phase**

Following Amendment 6, study data collection including laboratory tests, cardiovascular monitoring, physical examinations, tumor assessments, PROs, and ECOG status will cease when all subjects on study treatment have completed the treatment termination visit assessments as specified in the Time and Events Schedule for Amendment 6 or by 18 January 2018, whichever occurs first. For subjects continuing treatment with single-agent DOXIL, as per the local

standard of care, only serious adverse events should be reported to JR&D as outlined in Section 12.3.2.

#### **9.1.3.1. Clinical Laboratory Tests**

Blood samples for serum chemistry and hematology may be obtained from a central venous catheter or a peripheral vein. Blood samples will be obtained on Days 1, 8, and 15 for subjects assigned to Arm A and on Days 1, 8, 15, and 22 for subjects assigned to Arm B. Day 1 blood samples should be obtained before administration of the study drugs. For both treatment arms, CA-125 samples will be collected at screening, approximately every 8 weeks after randomization for the first 4 evaluations, then approximately every 12 weeks until disease progression is radiographically confirmed, and at the treatment termination visit. For subjects who terminate treatment prior to disease progression, CA-125 samples will be collected during the follow-up phase according to schedule until disease progression is radiographically confirmed, the start of subsequent anticancer therapy, withdrawal of subject consent, or the clinical cutoff date. All CA-125 sample collections should coincide ( $\pm 5$  days) with the scheduled tumor assessments. All blood samples are to be obtained within 2 days prior to drug administration on Day 1 and  $\pm 2$  days on Days 8 and 15 (Treatment Arm A) or Days 8, 15, and 22 (Treatment Arm B) of each treatment cycle. If a subject has an ANC of  $< 500/\mu\text{L}$ , the ANC for this subject should be repeated, at most 5 days later to document recovery to  $> 500/\mu\text{L}$ , and the scheduled visit can occur up to 3 days earlier in order to obtain the blood sample to perform this assessment.

Laboratory reports will be maintained at the study sites as source documents. Any clinically significant changes occurring during the study must be recorded on the adverse event page in the CRF.

#### **Serum Chemistry**

A sample of approximately 10 mL of venous blood will be collected for the following assessments: total protein, ALP, AST, ALT, CPK, total (direct and indirect) bilirubin, blood urea nitrogen (BUN), creatinine, sodium, potassium, glucose, and albumin.

#### **Hematology**

A sample of approximately 5 mL of venous blood will be collected for the following assessments: hemoglobin, ANC, white blood cell count (WBC), and platelet count.

#### **9.1.3.2. Cardiovascular Safety**

Left ventricular ejection fraction assessments (MUGA scans or 2D-ECHOs) will be performed for all subjects at screening (baseline), after an approximately  $100 \text{ mg}/\text{m}^2$  cumulative dose of planned anthracycline treatment with DOXIL (ie, after Cycle 3 for treatment Arm A and after Cycle 2 for treatment Arm B) and as part of end-of-treatment assessments (ie, end-of-treatment termination visit). In addition, those subjects who receive a total cumulative dose of anthracycline exceeding  $300 \text{ mg}/\text{m}^2$  (including previous and on-study treatments) or have a clinically significant history of cardiomyopathy should have follow-up LVEF assessments after every 2 cycles of therapy, or as clinically warranted. The same methodology (MUGA scans or

2D-ECHOs) should be used to assess scheduled LVEF assessments throughout the study. Additional LVEF assessments performed during the study should be reported as unscheduled LVEF assessments.

### **9.1.3.3. Physical Examination**

A physical exam is to be performed and the results recorded only once during screening.

### **9.1.3.4. Tumor Assessment**

Measurable disease and the response criteria used in this protocol are defined in the RECIST guidelines (Version 1.1) ([Attachment 2](#)) and will be based on radiologic assessment only.

Every effort should be made to ensure that the same radiographic method of disease assessment (computed tomography [CT] scans or magnetic resonance imaging [MRI]) be used throughout the study. Disease assessment procedures to evaluate objective response must be consistent with RECIST (Version 1.1) guidelines for radiologic assessment, as presented in [Attachment 2](#), RECIST Guidelines. The disease assessments should include, at a minimum, imaging of the chest (with lung views) abdomen, and pelvis. All disease assessments, including CA-125 measurements, will be performed within 30 days before randomization, every 8 weeks ( $\pm 5$  days) from the date of randomization for the first 4 assessments, and then every 12 weeks ( $\pm 5$  days) until disease progression is radiographically confirmed, the start of subsequent anticancer therapy, withdrawal of subject consent, or the clinical cutoff date. Disease assessments should be performed at the treatment termination visit and according to schedule thereafter if disease progression or follow-up therapy has not been documented. Every effort should be made to ensure that these assessments are done on the required date, although a window of  $\pm 5$  days will be accommodated.

In case of clinical progression, radiologic assessments should proceed according to the original Time and Events Schedule or as clinically indicated. The date of progression will be defined as the date of the first imaging study that documents progression.

Elevated CA-125 in the absence of radiographic progression is not to be considered evidence of disease progression. Therefore, it should not trigger an unscheduled assessment of tumor status nor result in treatment discontinuation. Other signs or symptoms deemed related to disease when suggestive of progression, including escalating pain not referable to another cause, increased ascites, protracted nausea and vomiting despite treatment, declining performance status, and examination findings consistent with disease progression, are valid reasons to consider an unscheduled assessment of tumor status. In this case, the assessment would include both imaging and CA-125. To the extent possible, it is important that all subjects have radiologic documentation of progression before study withdrawal or the initiation of follow-up therapy.

If a subject requests discontinuation of the study treatment but consents to continued evaluation, follow-up according to study procedure should be performed. In particular, tumor status assessment should be done according to the study timetable.

### 9.1.3.5. Patient Reported Outcomes Assessments

Health-related quality of life will be assessed using the quality of life questionnaire (QLQ) OV28 ([Attachment 3](#)). An additional PRO instrument, EQ-5D-5L ([Attachment 4](#)), will also be administered to perform preference based utility analysis. These questionnaires will be collected before any other tests or procedures are conducted on Day 1 of each treatment cycle and at the end-of-treatment evaluations. In addition, the EQ-5D-5L questionnaire will be collected approximately every 8 weeks thereafter until start of subsequent anticancer therapy.

### 9.1.3.6. Other Assessments

Eastern Cooperative Oncology Group performance status will be assessed during screening and at treatment discontinuation. Adverse events and changes in concomitant medications should be recorded at every visit.

## 9.1.4. Posttreatment Phase (Follow-Up)

### Termination of Treatment

As of Amendment 6, all subjects who are on study treatment should have treatment termination visit assessments as specified in the Time and Events Schedule for Amendment 6 (ie, within 30 days of the last dose of study drug) or by 18 January 2018, whichever occurs first.

For subjects who discontinue treatment for reasons other than radiographic disease progression, tumor assessments (including CA-125) will continue on schedule until: 1) disease progression is radiographically confirmed, 2) the subject withdraws consent, 3) the subject begins subsequent anticancer therapy, or 4) the study is terminated (ie, clinical cutoff). For subjects who discontinue study treatment, documentation of all subsequent anticancer therapy, survival status, and safety evaluations as outlined in the Time and Events Schedule will be required. Survival status should be recorded at least every 8 weeks for the first 2 years after the treatment termination visit and approximately every 12 weeks thereafter. Collection of survival status will continue until at least 514 deaths have been observed or until the clinical cutoff date. The access to study treatment will remain available for subjects who are consenting and eligible for treatment continuation. Once the study has been terminated, reporting will be limited to unexpected, drug-related serious adverse events during treatment or within 30 days of last dose of the study treatment.

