## 9.2. Efficacy

### 9.2.1. Evaluations

Efficacy will be assessed by determination of the OS, PFS, and ORR end points ([Attachment 2](#)).

Appropriate radiological disease assessments (CT scans or MRI) of the chest (with lung views), abdomen, and pelvis and will be performed within 30 days before randomization, approximately every 8 weeks ( $\pm 5$  days) after randomization for the first 4 assessments, and then every 12 weeks ( $\pm 5$  days) until disease progression is radiographically confirmed, the start of subsequent anticancer therapy, withdrawal of subject consent, or the clinical cutoff date (18 January 2018). Assessments must be done consistently (every 8 weeks [ $\pm 5$  days] for the first 4 assessments and then every 12 weeks [ $\pm 5$  days]) in both treatment arms to ensure an unbiased assessment of tumor response and progression.

CA-125 analysis will be done at screening, approximately every 8 weeks after randomization for the first 4 evaluations and then approximately every 12 weeks until disease progression is radiographically confirmed, the start of subsequent anticancer therapy, withdrawal of subject consent, or the clinical cutoff date (18 January 2018). CA-125 sample collections should coincide ( $\pm 5$  days) with the scheduled tumor assessments. Analyses of CA-125 will be done at a local laboratory.

CA-125 shall not be used as a basis to assess disease response or progression during study treatment and should not guide treatment decisions.

Survival follow up will continue for all enrolled subjects until at least 514 deaths are observed or until the clinical cutoff date.

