## 12. ADVERSE EVENT REPORTING

Following Amendment 6, only serious adverse events for subjects continuing to receive single-agent DOXIL should be reported to JR&D as outlined in Section 12.3.2.

Timely, accurate, and complete reporting and analysis of safety information from clinical studies are crucial for the protection of subjects, investigators, and the sponsor, and are mandated by regulatory agencies worldwide. The sponsor has established Standard Operating Procedures in conformity with regulatory requirements worldwide to ensure appropriate reporting of safety information; all clinical studies conducted by the sponsor or its affiliates will be conducted in accordance with those procedures.

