**12.3. Procedures****12.3.1. All Adverse Events**

All adverse events and special reporting situations, whether serious or non-serious, will be reported from the time a signed and dated ICF is obtained until 30 days after the administration of the last dose of study drug or until the scheduled treatment termination visit on or prior to 18 January 2018. Any drug-related Grade 3 or 4 toxicities will be followed by the investigator until Grade 2 or less, for a maximum of 6 months after the last dose of study drug, or until the scheduled treatment termination visit on or prior to 18 January 2018, whichever occurs first. Grade 2 to 4 liver or cardiac toxicities will be monitored until Grade 1 or less, for a maximum of 6 months after the last dose of study drug, or until the scheduled treatment termination visit on or prior to 18 January 2018, whichever occurs first.

Serious adverse events, including those spontaneously reported to the investigator within 30 days after the last dose of study drug, must be reported using the Serious Adverse Event Form. The sponsor will evaluate any safety information that is spontaneously reported by an investigator beyond the time frame specified in the protocol. All events that meet the definition of a serious adverse event will be reported as serious adverse events, regardless of whether they are protocol-specific assessments.

All adverse events, regardless of seriousness, severity, or presumed relationship to study drug, must be recorded using medical terminology in the source document and the CRF. Whenever possible, diagnoses should be given when signs and symptoms are due to a common etiology (eg, cough, runny nose, sneezing, sore throat, and head congestion should be reported as "upper respiratory infection"). Investigators must record in the CRF their opinion concerning the

relationship of the adverse event to study therapy. All measures required for adverse event management must be recorded in the source document and reported according to sponsor instructions.

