### **12.3.2. Serious Adverse Events**

All serious adverse events occurring during the study must be reported to the appropriate sponsor contact person by study-site personnel within 24 hours of their knowledge of the event.

Information regarding serious adverse events will be transmitted to the sponsor using the Serious Adverse Event Form, which must be completed and signed by a physician from the study site, and transmitted to the sponsor within 24 hours. The initial and follow-up reports of a serious adverse event should be made by facsimile (fax).

All serious adverse events that have not resolved upon discontinuation of the subject's participation in the study, must be followed until any of the following occurs:

- The event resolves
- The event stabilizes (as noted in Section 9.5).
- The event returns to baseline, if a baseline value/status is available
- The event can be attributed to agents other than the study drug or to factors unrelated to study conduct
- It becomes unlikely that any additional information can be obtained (subject or health care practitioner refusal to provide additional information, lost to follow-up after demonstration of due diligence with follow-up efforts)

- The study ends (when post-trial access to DOXIL is available for subjects remaining on single-agent DOXIL or until disease progression, whichever occurs first).

Suspected transmission of an infectious agent by a medicinal product will be reported as a serious adverse event. Any event requiring hospitalization (or prolongation of hospitalization) that occurs during the course of a subject's participation in a study must be reported as a serious adverse event, except hospitalizations for the following:

- Hospitalizations not intended to treat an acute illness or adverse event (eg, social reasons such as pending placement in long-term care facility).
- Surgery or procedure planned before entry into the study (must be documented in the CRF). Note: Hospitalizations that were planned before the signing of the ICF, and where the underlying condition for which the hospitalization was planned has not worsened, will not be considered serious adverse events. Any adverse event that results in a prolongation of the originally planned hospitalization is to be reported as a new serious adverse event.
- For reasons described in the protocol, eg, study drug administration, protocol-required testing.

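### Protocol Section 9.1.4 limits post-cutoff reporting to unexpected, drug-related SAEs, while Sections 12 and 12.3.2 apply no such filter

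*Protocol*

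**What the plan says.** **The filtered rule.** Protocol Section 9.1.4, under Termination of Treatment, sets the scope that applies after termination: "reporting will be limited to unexpected, drug-related serious adverse events during treatment or within 30 days of last dose". Earlier in that paragraph, the list of reasons for ending tumor assessments has as its last item "4) the study is terminated (ie, clinical cutoff", so termination there means the clinical cutoff. Section 9.2.1 dates it: "or the clinical cutoff date (18 January 2018".

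**The unfiltered rule.** Section 12 opens by saying that after Amendment 6 "only serious adverse events for subjects continuing to receive single-agent DOXIL should be reported to JR&D", and refers to Section 12.3.2. Section 12.3.2 says: "All serious adverse events occurring during the study must be reported to the appropriate sponsor contact person by study-site personnel within 24 hours". Neither place tests for expectedness or causality. The unfiltered rule for subjects continuing DOXIL also appears in the Synopsis (study design and safety evaluations), Sections 3.1, 9, 9.1.3, 9.5 and 10.1, Attachment 7, and SAP Section 1.2.

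**The end of the study.** Among its end points for following unresolved SAEs, Section 12.3.2 gives "The study ends (when post-trial access to DOXIL is available for subjects remaining on single-agent DOXIL or until disease progression, whichever occurs first".

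**The 30-day rule.** Section 12.3.1 adds: "Serious adverse events, including those spontaneously reported to the investigator within 30 days after the last dose of study drug, must be reported". That sentence carries no cutoff date.

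**The concern.** Amendment 6 stops trabectedin but lets subjects stay on sponsor-supplied DOXIL while they benefit. Section 9.5 ends the collection of non-serious adverse events, laboratory tests, cardiovascular monitoring, vital signs and physical examinations at the termination visit assessments or by 18 January 2018. Section 9.1.4 says that follow-up data are no longer collected. From then on, SAE reports are all the safety information the sponsor receives on these subjects.

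On that same date the protocol gives sites two instructions. Under Section 9.1.4 the site would first judge whether an SAE is unexpected and drug-related, and would not report it if either answer is no. Under Sections 12 and 12.3.2 it would report the event within 24 hours regardless. If sites differ in which they follow, SAE reporting is incomplete in a way the sponsor cannot see.

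**Working it through.** No sample size, power or event figure enters this point, so the check is a comparison of text.

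**Step 1. Do the rules apply at the same time?** Section 9.1.4 starts its rule at termination and, within the paragraph, equates that with the clinical cutoff of 18 January 2018. The Synopsis (safety evaluations) ties the unfiltered rule to the same date. Section 12.2 also says that after 18 January 2018 a special reporting situation meeting the SAE criteria is still reported, again without a filter. The periods coincide.

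**Step 2. Could 'terminated' in Section 9.1.4 mean the later study end in Section 12.3.2?** That would remove the overlap, but Section 9.1.4 supplies its own meaning. The sentence just before the filtered rule says access to study treatment remains available, and the rule itself covers events during treatment, so it contemplates subjects still being dosed.

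**Step 3. Could 'during the study' in Section 12.3.2 stop at the cutoff?** Not on that section's own terms: its study end is post-trial access or progression, and the Amendment 6 text sends post-cutoff reporting to it. The wider protocol is not consistent, however. Section 3.1 lists the clinical cutoff among the events that end the study, and Section 17.9.1 uses the last visit of the last subject.

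**Step 4. Which SAEs differ?** For a subject on single-agent DOXIL after 18 January 2018:

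| SAE | Section 9.1.4 | Sections 12 and 12.3.2 |
|---|---|---|
| Unexpected, drug-related | Report | Report |
| Unexpected, not drug-related | Do not report | Report |
| Expected, drug-related | Do not report | Report |
| Expected, not drug-related | Do not report | Report |

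The rules agree in one class of four. Section 12.3.2 also treats the cause of any death within 30 days of the last dose as an SAE, whether or not it is expected or drug-associated, so the conflict reaches deaths.

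**Step 5. Is there a precedence rule?** No statement was found that ranks one section above another. Section 9.1.4 is current text: its subsection opens with an Amendment 6 paragraph, and the filtered sentence follows in the next paragraph.

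**Step 6. Who is covered?** Section 12 names subjects continuing single-agent DOXIL. Two groups fit that wording poorly.

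- *Subjects who stop all treatment.* The 30 days after a dose on 19 December 2017 end on 18 January 2018 (12 days to 31 December, plus 18), so any later last dose has a window running past the cutoff. Amendment 6 is dated 9 January 2018 and Arm A cycles last 21 days; 9 January less 21 days is 19 December. An Arm A subject still on treatment at that date and dosed on schedule was therefore last dosed on or after about 19 December. Section 12.3.1 requires her SAEs within 30 days; the word *only* in Section 12 can be read as excluding them.
- *Subjects in screening.* Sections 3.2 and 4 and Attachment 7 allow them to start DOXIL without randomization. Whether they count as *continuing* is unclear.

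**The case against.** The strongest reply is that this is one leftover sentence. The unfiltered rule is repeated across the protocol and SAP, usually with a pointer to Section 12.3.2; the filtered sentence appears once, outside the adverse event section. A site reading the whole protocol would most likely report every SAE. SAP Section 2.2 fixes the final efficacy and safety analysis at 18 January 2018, so later SAEs do not enter it. Both points stand. They limit the consequence to pharmacovigilance in a residual group, but do not tell a site reading Section 9.1.4 that the sentence is void.

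Four stronger readings are tempting and are not supported:

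- *Three competing SAE scopes.* Sections 12.3.1 and 12 read largely as successive periods of one scheme: all adverse events up to 18 January 2018, then SAEs only. The firm conflict is Section 9.1.4 against that scheme.
- *A subject who stops treatment is left out.* The 30-day sentence in Section 12.3.1 and the death rule in Section 12.3.2 cover her. The wording of Section 12 makes this ambiguous; it does not make it an omission.
- *SAE reports are the only surveillance for Arm A subjects coming off trabectedin.* Before the cutoff they are not. The Amendment 6 schedule includes adverse events, ECG, LVEF, hematology and chemistry at the termination visit, and Sections 9.5 and 12.3.1 keep toxicity follow-up running to 18 January 2018.
- *The 8% Grade 3 or 4 neutropenic fever in the predecessor study shows the size of the loss.* That figure is from the combination arm, and trabectedin has stopped; the monotherapy figure is 2%. Both are incidences over a whole study, not SAE rates. Expectedness is judged against reference safety information that is not in these documents (Section 12.1.1).

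**Conclusion.** The contradiction is real and lies in current text. After 18 January 2018, Section 9.1.4 removes from reporting every SAE that is expected or judged not drug-related, while Sections 12 and 12.3.2 and the Amendment 6 text keep them for subjects continuing single-agent DOXIL. It should be corrected, because SAE reporting is then the only safety stream for these subjects.

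The size cannot be stated: the documents give neither the number of subjects who stay on DOXIL nor an SAE rate for them. The conclusion rests on taking Section 9.1.4's own equation of termination with clinical cutoff at face value, and on the absence of any precedence statement. It does not bear on the efficacy results or on the safety analysis at the cutoff.

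The coverage question in Section 12, on subjects who have stopped and subjects entering from screening, is a secondary matter of clarity.

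**What to change.** 1. In Section 9.1.4, delete the sentence that limits reporting after termination, or align it with Section 12.3.2.
2. Give *study terminated* and *study ends* one definition, used alike in Sections 3.1, 9.1.4, 12.3.2 and 17.9.1, and distinguish it from the clinical cutoff for data collection.
3. As a clarification, reconcile the opening of Section 12 with the 30-day SAE rule in Section 12.3.1, and say whether subjects who start DOXIL from screening under Attachment 7 are included.

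The cost is a wording change in the amendment and, where a site would have followed Section 9.1.4, some additional SAE forms. No visit, assessment or analysis changes.
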